Motivating Change in Aging African American Smokers - Testing Messages

NCT05819086

Initial IRB Approval: 2/15/2023

Document Created: 9/6/2024

Motivating Change in Aging Smokers – 2 (MCAS Aim 2)

PI: [name]

Study Purpose

The purpose of this research is to evaluate messages that motivate older smokers to make quit attempts using evidence based smoking treatments (EBSTs).

Background

An estimated 5.8 million people have Alzheimer's disease and related dementias (ADRD) in the U.S., costing \$290 billion per year. The incidence of ADRD is expected to triple by 2050, costing an estimated \$1.1 trillion per year. Due to the rapid growth and tremendous impact of this disease, focus has shifted towards targeting modifiable risk factors to prevent and slow the development of ADRD, potentially preventing approximately 40% of ADRD cases². A candidate risk factor, cigarette smoking, is the leading preventable cause of death and disability in the U.S., resulting in 480,000 deaths and costing over \$300 billion each year. Epidemiological studies show that cigarette smoking is prospectively associated with a 70% increased risk of Alzheimer's disease (AD) dementia onset, accounting for at least 13.9% of ADRD cases. Smoking directly increases the likelihood and severity of at least five risk factors for ADRD onset (i.e., diabetes, hypertension, stroke, heart disease, and high cholesterol). Smoking cessation can lower these risk factors, even among an aging population.

Regardless of genetic risk, healthy lifestyle modifications such as smoking cessation can cut the risk of ADRD in half. Due to the known relations between smoking, other ADRD risk factors, and ADRD, the World Health Organization, Institute of Medicine, and Alzheimer's Association state that smoking cessation is among the top priorities for reducing cognitive decline and preventing onset of dementia. Fortunately, evidence-based smoking treatments (EBSTs) exist that can double or triple cessation success. Older adult smokers are at especially high risk for ADRD. Currently, there are 19 million smokers ages 45 and older. Given the predicted doubling of older adults in the next 25 years, helping older smokers quit is a vital public health priority. Unfortunately, older smokers are half as likely to attempt to quit smoking compared to younger adults⁴⁰. Lower cessation efforts in older smokers may be a function of both clinician inaction and dysfunctional beliefs/motivational deficits of older smokers. Compared to younger adults, older smokers are less likely to receive advice to quit or be offered EBSTs (e.g., pharmacotherapy, counseling) by healthcare professionals. Moreover, older smokers' doubts about the benefits of quitting later in life and the efficacy of smoking cessation interventions may reduce older smokers' motivation to quit¹³. Importantly, older smokers who do attempt to quit are more likely to maintain abstinence than younger smokers when using EBSTs. The chief obstacle to reducing smoking among older adults does not appear to be treatment efficacy, but rather failing to motivate this underserved population to make quit attempts using EBSTs.

According to the Health Belief Model, impactful motivational messages for older smokers should focus on threats they perceive as important and personally relevant and messages should be offered with a feasible, effective course of action to address the health threat. Older adults' greatest aging-related fear is cognitive decline and developing dementia⁴⁵⁻⁴⁷; it is both important and relevant. The link between smoking and ADRD risk factors and the availability of EBSTs offers an effective strategy to respond to

this threat. Unfortunately, the indirect relation between smoking and ADRD risk expressed via known ADRD risk factors has not been clearly articulated to the general or medical community, and is not used as a motivator for smoking cessation. Providing this message within the health care system, where older smokers can access EBSTs at little or no cost, and where they spend a disproportionate amount of their time, will increase use of EBSTs. Building novel interventions for translation will facilitate more rapid dissemination and subsequent impact on public health. The overarching objective of this proposal is to develop and test a readily translatable Stage 1 motivational intervention for smoking cessation in older adults consisting of: (1) a novel patient-informed motivational message promoting smoking cessation; and (2) ready access to EBSTs for smoking cessation within a healthcare setting. This responds to two of NIA's goals: (1) develop effective interventions to maintain health, well-being, and function and prevent age-related diseases/disabilities; and (2) disseminate information to the public, medical, and scientific communities. This project will evaluate the motivational impact of 2 message packages developed from a previous study (IRB# 2020-1429).

Study Procedures

After providing study information, participants will be randomized to one of three unique message packages: (1) Message A (hope-based video message and flyer; n = 275), (2) Message B (fear-based video message and flyer; n = 275), or (3) Control Message C (water advertisement video and flyer; n = 275). These messages will be presented as part of a (~15 minute) online survey, conducted via Qualtrics (a secure, web-based application designed to support data capture for research studies) and collected by Centiment LLC. The survey will first assess demographic characteristics (i.e., age, race, ethnicity, gender identity, income level, education level), psychiatric history (i.e., self-report of current or lifetime psychiatric diagnosis), smoking history (e.g., cigarettes smoked per day, age of smoking onset) and current motivation to quit smoking. Participants will then view their randomized message package (A, B, or C), and will be asked to rate their emotional response to this message, and the impact of the presented messages on motivation to quit (only in Message A and B conditions) and behavior change mechanisms outlined in the HBM: perceived susceptibility, perceived severity, perceived benefits, perceived barriers, self-efficacy. Upon completion, participants will be paid for their time and effort by Centiment LLC, through secure PayPal payments. Per projections from Centiment, in order to recruit the planned 825 participants, participants will be compensated for their time and effort based on Centiment LLC's approved compensation strategy.

Eligibility Criteria

Eligibility criteria include self-identifying as African American or Black (can identify as AA along with other race), current smoker (defined as smoking >100 cigarettes in their lifetime and currently smoking cigarettes 'some days' or 'everyday'), able to read and write in English, ages 50-80, no self-reported history of MCI or dementia.

Recruitment

Participants selected for this study will be recruited to represent the national (U.S.) populations of older adults, particularly by gender (approximately 50 percent female ± 10 percent). Participants will be recruited via text message from a pre-existing pool of potential participants within the U.S. using a market research company (Centiment, LLC). Centiment is a large market research company with a pool of thousands of pre-existing individuals who are solicited to engage in various studies Centiment is

contracted to support. The company has reach in over 100 countries with a vast array of background demographic information on potential participants including race, gender, age, medical history (self-reported), and behaviors (including smoking status as identified in the Participants section). Potentially eligible participants for this study from Centiment's pool of individuals (based on eligibility criteria described in the section above) will be sent an invitation via text message to complete the study survey, those who then respond and complete the survey will be considered enrolled in this study.

Statistical Analysis Plan

Data analysis will be performed using IBM SPSS Statistics. Chi-square tests of independent and Analyses of Variance (ANOVAs) will be used to confirm randomization resulted in no significant differences between groups in terms of demographics, smoking-related variables, and psychiatric history. ANCOVA tests with planned contrasts will be used for primary analyses. Primary analyses will control for baseline values (of motivation and intention to quit, respectively) due to the risk of bias of baseline variables. Secondary analyses will compare the messages to each other using ANOVAs to examine the effect of condition on perceived message effectiveness, reactance, and informativeness. Analyses of emotionality will use ANOVAs. Lastly, Benjamin-Hochberg corrections, which are less susceptible to type II error than other forms of statistical corrections, will control for false discovery rate (FDR) for covariate-corrected analyses involving emotionality.

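### The primary ANCOVAs imply post-message motivation and intention scores, but the Procedures describe neither score for control arm C and do not describe intention in any arm

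*Combined protocol and SAP*

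**What the plan says.** On the primary analysis, the Statistical Analysis Plan states: "ANCOVA tests with planned contrasts will be used for primary analyses". It adds: "Primary analyses will control for baseline values (of motivation and intention to quit, respectively) due to the risk of bias of baseline variables". It names neither the dependent variables nor the contrasts. Secondary ANOVAs compare the messages "to examine the effect of condition on perceived message effectiveness, reactance, and informativeness", and a further sentence says: "Analyses of emotionality will use ANOVAs".

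Study Procedures give the order of the survey. Before the message, all participants report demographics, psychiatric history, "smoking history (e.g., cigarettes smoked per day, age of smoking onset) and current motivation to quit smoking". The next step is: "Participants will then view their randomized message package (A, B, or C), and will be asked to rate their emotional response to this message". Two further post-message ratings follow in the same sentence. One is "the impact of the presented messages on motivation to quit (only in Message A and B conditions". The other covers the "behavior change mechanisms outlined in the HBM: perceived susceptibility, perceived severity, perceived benefits, perceived barriers, self-efficacy".

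Intention to quit appears only in the Statistical Analysis Plan sentence on baseline adjustment.

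**The concern.** An ANCOVA that controls for the baseline value of a construct normally has the later value of that construct as its outcome. The analysis plan therefore presupposes motivation and intention scores both before and after the message. The Procedures describe motivation only once as a score, at baseline. What they describe afterwards is a rating of the message's effect on motivation, and that rating is expressly withheld from the control arm. Intention is not described at all.

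Arm C is the reference for a study whose stated purpose is to evaluate messages that motivate quit attempts. Without a post-message score in arm C, the change seen in A or B cannot be separated from what the survey itself or the passage of a few minutes would produce. Only one survey is described, with no later contact, so an item that is not asked cannot be recovered.

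**Working it through.** **1. The plan's own figure.** Three arms of 275 give 3 × 275 = 825, which matches the planned total in Study Procedures. Arm C is 275/825 = 33.3%. Arms A and B together are 550/825 = 66.7%. No alpha, effect size or correlation is needed for this check.

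**2. Outcomes in the analysis plan set against measures in the Procedures.**

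| Construct in the Statistical Analysis Plan | Role there | Described before the message | Described after the message |
|---|---|---|---|
| Motivation to quit | Primary (implied) | All arms | Impact rating, A and B only |
| Intention to quit | Primary (implied) | Not described | Not described |
| Perceived message effectiveness | Secondary | Not applicable | Not described under that name |
| Reactance | Secondary | Not applicable | Not described |
| Informativeness | Secondary | Not applicable | Not described |
| Emotionality | Further analysis | Not applicable | All arms |

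**3. What the primary model needs.** For each outcome, the model is: post-message score = arm effect + slope × baseline score + error. A contrast of A or B with C needs post-message scores in both arms of the pair.

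- Motivation: a baseline is described for all 825. The only described post-message measure would come from 550 participants in A and B and from 0 of 275 in C. On that measure the arm effect for C cannot be estimated.
- Intention: neither the covariate nor the outcome is described in any arm, so the model cannot be set up from the Procedures.

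**4. Two readings of the A/B-only rating.**

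- It is the motivation outcome. Then it supports A against B only. It also does not appear to repeat the baseline item: one asks how motivated the person is, the other what the message did. No item wording is given, so this is the natural reading, not an established fact.
- It is the secondary perceived-effectiveness measure under another name. Then no post-message motivation score is described in any arm.

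On both readings, arm C has no described post-message motivation value.

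**5. What else could stand in.** Emotional response and, on the natural reading of the sentence, the Health Belief Model ratings carry no arm restriction. They would allow comparison with control, but neither is a measure of motivation or intention.

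**The case against.** The strongest reply is that this is an incomplete description and that the two sections do not truly contradict each other. The Procedures restrict one item, the impact rating. They do not say that post-message motivation is withheld from controls. The restriction is sensible for that item, since asking how a water advertisement affected motivation to quit makes little sense. If the rating is the secondary effectiveness measure, its restriction says nothing about the primary analysis. The Procedures also omit reactance and informativeness, which the analysis plan uses, so they are clearly abbreviated. The absence of baseline intention, a named covariate, points the same way.

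Much of this stands. A reader might infer that the survey lacks these items, that the primary comparison with control is impossible, or that the investigators chose not to measure motivation in controls. The documents support none of these; they support only that the items are not described. Nor can one count how many primary contrasts would be lost, because the plan names no contrasts and any denominator would be the reader's own.

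Two things survive. No repeat item is stated for any arm, and the one arm restriction that is stated falls on the construct of a primary analysis. An abbreviated list explains a missing item, but it does not tell someone building or auditing the survey that arm C must receive a motivation item after the message.

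**Conclusion.** The point holds as a failure of the two sections to agree on the implied primary outcomes. Followed as written, the survey would give no post-message motivation or intention score for the 275 controls (33.3% of 825). Neither message could then be compared with control on those outcomes. If repeat items are already in the survey for all arms, no data are lost and the defect is one of wording. The documents do not show which case applies.

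The conclusion rests on one inference: that adjusting for baseline motivation and intention, respectively, means two models whose outcomes are the matching post-message scores. The plan does not say so outright, and that is part of what needs correcting. A reader might also take A against C and B against C to be the planned contrasts. Given the study purpose that is the natural choice, but the plan does not state it.

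This should be settled before any primary claim is made, because it concerns the primary outcome in the control arm, the described survey happens only once, and the correction is nearly free.

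**What to change.** - Ask the same motivation-to-quit and intention-to-quit items before, and immediately after, the video and flyer in all three arms.
- In the Statistical Analysis Plan, name the two post-message scores as the primary outcomes, each adjusted for its own baseline.
- Name the planned contrasts. A against C and B against C fit the study purpose.
- In Study Procedures, list each measure with its arms and time of collection, including the secondary measures now missing.
- Label the A/B-only impact rating as secondary. If it is the perceived-effectiveness measure, say so.
- If the repeat items are already in the survey, state that in Study Procedures.
- If the survey has already been fielded, which the documents do not show, state what was collected, in which arms and when, and limit the primary claims to that.

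The cost is a few short items repeated in a survey of about 15 minutes and edits to two sections, with no added participants. If the items are already there, the cost is wording only.

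### Baseline significance tests cannot confirm randomisation, and the secondary and emotionality models name no baseline covariate although baseline motivation to quit is collected before exposure

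*Combined protocol and SAP*

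**What the plan says.** The Statistical Analysis Plan section begins with chi-square tests and ANOVAs that "will be used to confirm randomization resulted in no significant differences between groups" "in terms of demographics, smoking-related variables, and psychiatric history". It gives no significance level for these tests, no number of tests, and no action if one is significant.

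The variables are listed under Study Procedures: six demographic items ("age, race, ethnicity, gender identity, income level, education level"), psychiatric history ("self-report of current or lifetime psychiatric diagnosis"), and "smoking history (e.g., cigarettes smoked per day, age of smoking onset) and current motivation to quit smoking". All are asked before the message is shown.

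The models are then set out as follows:

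- Primary outcomes: ANCOVA, with motivation and intention to quit each adjusted for its own baseline value.
- Secondary outcomes (how effective and informative the message seems, and reactance to it): ANOVA, with no covariate mentioned.
- Emotionality: ANOVA. The next sentence, however, applies a false discovery rate correction "for covariate-corrected analyses involving emotionality", and does not say what those covariates are.

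Under Study Procedures, "participants will be randomized to one of three unique message packages", with 275 planned per arm. Under Recruitment, only people who complete the survey count as enrolled.

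**The concern.** A test of baseline difference asks whether the observed imbalance is larger than chance would usually give. When allocation is random and everyone randomised is analysed, chance is the only explanation, so the test has nothing to find. Absence of significance is not evidence that allocation worked.

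Two things are at stake. First, a sound trial can easily appear to fail its own check, and the plan does not say what happens then. Nearby text speaks of covariate correction without naming covariates, and it justifies the primary adjustment by bias at baseline, not by how well a covariate predicts the outcome. An analyst could therefore choose covariates after seeing which tests were significant.

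Second, the plan passes over a simple gain. Baseline motivation to quit is already measured before exposure, yet the secondary models do not use it, and the emotionality models do not say whether they do. Adjustment fixed in advance can sharpen these comparisons without more participants.

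**Working it through.** The documents give no error rate, alpha, power or effect size on this point, so there is no stated figure to reproduce. The planned total is consistent: 3 × 275 = 825.

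**Step 1. Number of variables tested.** Study Procedures names 6 demographic, 1 psychiatric and 2 smoking-history variables, so k = 9. The smoking list is open-ended, and the psychiatric item could be split into current and lifetime, so k could be larger. Baseline motivation is not clearly within the tested domains and is not counted.

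**Step 2. Chance of at least one significant test under sound randomisation.** Alpha is assumed to be 0.05 per test. With independent tests the chance is 1 − (1 − alpha)^k:

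- k = 8: 1 − 0.95^8 = 33.7%
- k = 9: 1 − 0.95^9 = 37.0%
- k = 10: 1 − 0.95^10 = 40.1%
- k = 12: 1 − 0.95^12 = 46.0%

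The assumed alpha matters. With k = 9 the figure is 8.7% at alpha 0.01 and 61.3% at alpha 0.10.

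**Step 3. Allow for correlation.** Baseline variables are unlikely to be independent; income and education are an obvious pair. A simulation of three-arm F tests at 275 per arm, with equal pairwise correlation and 20,000 replicates, gave for k = 9:

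- correlation 0.3: 32.8%
- correlation 0.5: 27.3%
- correlation 0.7: 20.7%

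At zero correlation the simulation gave 36.1%, close to the exact 37.0%.

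**Step 4. Compare the model statements.** An ANOVA by condition and a covariate-corrected analysis are different models. The plan gives both descriptions to emotionality, with neither a covariate nor a rule for choosing one. No sentence connects the baseline tests to that choice, and no sentence excludes it.

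**Step 5. Value of adjusting for a baseline covariate.** If r is the within-arm correlation between covariate and outcome, adjustment multiplies the residual variance by 1 − r². The unadjusted sample size giving the same precision is 275 / (1 − r²) per arm. The documents do not give r, so a range is shown:

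- r = 0.1: 275 / 0.99 = 278
- r = 0.3: 275 / 0.91 = 302
- r = 0.5: 275 / 0.75 = 367

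**Step 6. Cost in degrees of freedom.** A three-arm ANOVA on 825 people leaves 825 − 3 = 822 residual degrees of freedom. Each single-parameter covariate uses one.

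**The case against.** The strongest defence is that nothing in the plan depends on the baseline tests. The primary covariates are fixed whatever the tests show, so the primary results are not threatened. That stands. A reader might infer that the tests are the only place from which the emotionality covariates could come. The documents do not support this: the same section names baseline motivation and intention for the primary models, and either could be reused, as could other survey items chosen on substantive grounds. Test-driven selection is a possibility left open, not a stated rule.

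A second defence is that imbalance in the analysed set need not be pure chance. Only completers count as enrolled, and completion comes after randomisation and after a hopeful, frightening or neutral message. Drop-out that differs by arm could produce real baseline differences. This also stands, and it rules out saying that every significant test is a chance finding. But the plan does not give the tests that purpose, and counts randomised and completed per arm would show differential completion more directly.

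Third, a flat statement that the check fails about 40% of the time would be too strong. It needs about ten independent tests at alpha 0.05, and the plan states neither number. Race also adds little as a test, since every participant must identify as African American or Black; leaving it out gives k = 8.

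Fourth, the precision gain may be small. Reactance, informativeness and emotion are reactions to a message, not repeat measures of motivation, so a correlation near 0.1 is possible and the gain would then be negligible.

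**Conclusion.** The point holds in a limited form. Testing baseline differences does not serve the purpose that the plan gives it, and in a sound trial the chance of at least one significant result is roughly 21% to 37% for the nine named variables. That range assumes alpha 0.05 and pairwise correlations between 0.7 and zero.

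Removing the tests would by itself be little more than a wording change. The substantive part is that the secondary models are unadjusted and the emotionality models undefined, while a pre-exposure baseline measure is available. Adjusting for it would be worth between 3 and 92 extra participants per arm (278 − 275 and 367 − 275) for r from 0.1 to 0.5, a range assumed here.

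A reader might go further and infer that the emotionality models certainly omit prognostic covariates. The text does not settle that, because it does not say what those models adjust for. Nor does the point call for one common covariate set in every model: if that set omitted baseline intention, the intention analysis would lose the adjustment that the plan already specifies for it.

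**What to change.** Amend the Statistical Analysis Plan section as follows:

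- Keep the primary ANCOVAs with their outcome-specific baseline covariates: motivation for the motivation outcome and intention for the intention outcome.
- Change the secondary and emotionality ANOVAs to ANCOVAs. Name their covariates in advance, include baseline motivation to quit, and use the set whatever imbalance is seen. Any further covariates are the sponsor's choice, on the grounds that they predict the outcome.
- Use one description of the emotionality model throughout, so that the false discovery rate correction refers to a defined set of analyses.
- State that no covariate will be added or dropped because of a baseline test.
- Replace the balance tests with a table of baseline characteristics by condition without p-values, and report the numbers randomised and completed in each arm.

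The cost is SAP wording and a few degrees of freedom out of about 820. The baseline motivation item is already in the survey, so this covariate needs no new data collection.

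### Primary ANCOVA contrasts and emotionality ANOVAs would by default pool one residual variance over two message arms and a water-advert arm; the plan should use contrasts robust to unequal variances

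*Combined protocol and SAP*

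**What the plan says.** The Statistical Analysis Plan states that "ANCOVA tests with planned contrasts will be used for primary analyses", and that "Primary analyses will control for baseline values (of motivation and intention to quit, respectively"). On emotion ratings it states that "Analyses of emotionality will use ANOVAs". Secondary ANOVAs compare the messages on perceived effectiveness, reactance and informativeness. The software is SPSS. The plan does not list the contrasts, name the error term, or mention a variance check, a Welch test, robust standard errors or arm-specific variances.

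Study Procedures defines three arms: "Message A (hope-based video message and flyer; n = 275"), "Message B (fear-based video message and flyer; n = 275") and "Control Message C (water advertisement video and flyer; n = 275"). All participants see their assigned package and then rate their emotional response, so emotionality is measured in all three arms. For motivation the text is less clear. It has participants rate "the impact of the presented messages on motivation to quit (only in Message A and B conditions").

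The documents give no outcome scale, SD, significance level or power calculation.

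**The concern.** An ANCOVA or ANOVA with contrasts assumes one residual variance in all arms unless the plan says otherwise, and every contrast's standard error is built from that pooled value.

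This design gives reason to doubt the assumption. Arm C watches an unrelated advert inside a survey of about 15 minutes, so answers about quitting may largely repeat the baseline. In arms A and B people are meant to move, and may move by different amounts. Emotional reactions to an advert may likewise vary less than reactions to a hope or fear message, although no emotion scale is given to judge that by.

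If variances differ, the overall F test is fairly robust because the arms are equal in size, but single contrasts are not. Some would reject too often at the nominal level, and others would have intervals that are too wide and lose power.

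**Working it through.** **Inputs from the documents.** 275 per arm and 825 in total (Study Procedures); 3 × 275 = 825 agrees. The choice of 275 cannot be reproduced, because no effect size, SD, alpha or power is given.

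**Assumptions.** Two-sided nominal alpha of 0.05. A and B have the same residual variance, set to 1. Arm C has residual variance v. The documents give no value for v, so a range is shown.

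**Formulas, equal n.** The pooled residual variance is (2 + v)/3. The ratio of the pooled SE to the true SE is:

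- A vs B: true variance proportional to 2, pooled 2(2 + v)/3; ratio √[(2 + v)/3]
- one message vs C: true 1 + v, pooled 2(2 + v)/3; ratio √[2(2 + v)/(3(1 + v))]
- average of A and B vs C: true 0.5 + v, pooled (2 + v)/2; ratio √[(2 + v)/(1 + 2v)]

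The true type I error is 2[1 − Φ(1.96 × ratio)]. A contrast that would have 80% power with the correct SE has power Φ(2.80 − 1.96 × ratio).

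**Example, v = 0.5.** The A vs B ratio is √(2.5/3) = 0.913. Then 1.96 × 0.913 = 1.789, and the type I error is 7.4%. The A vs C ratio is √(5/4.5) = 1.054, so the interval is 5% too wide.

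| v | A vs B: SE ratio | A vs B: type I error | A vs C: SE ratio | A vs C: power | Average vs C: SE ratio |
|---|---|---|---|---|---|
| 1 | 1.000 | 5.0% | 1.000 | 80% | 1.000 |
| 0.75 | 0.957 | 6.1% | 1.024 | 79% | 1.049 |
| 0.5 | 0.913 | 7.4% | 1.054 | 77% | 1.118 |
| 0.25 | 0.866 | 9.0% | 1.095 | 74% | 1.225 |
| 1.56 (message SD 0.8 × control SD) | 1.090 | 3.3% | 0.963 | 82% | 0.929 |

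In the last row the control arm is the more variable one. A vs B becomes conservative, and A vs C has a type I error of 5.9%.

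**Unequal A and B.** With SDs of 1.5, 0.8 and 1.0 in A, B and C, the pooled variance is (2.25 + 0.64 + 1)/3 = 1.297. The A vs C ratio is √(2.593/3.25) = 0.893 (too narrow) and the B vs C ratio is √(2.593/1.64) = 1.257 (too wide).

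**Which direction?** On an assumed 1–10 scale, simulated message/control residual SD ratios ran from 0.87, where scores in the message arms pile up at the ceiling, to 1.36, where responses to the messages vary. Those ends correspond to v of about 1.33 and 0.54. Type I error for A vs B then runs from 3.9% to 7.1%, and the A vs C interval from 2% too narrow to 5% too wide.

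**Check of the remedy.** In a three-arm ANCOVA simulation with 275 per arm, 4,000 replicates and message/control SD ratios of 0.8 to 2, HC3 standard errors gave type I error of about 4.4% to 5.5% for all three contrasts. At an SD ratio of 1.5, A vs B had 8.0% with pooled error and 5.3% with HC3.

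**The case against.** The strongest case against the point is that it rests on a default and not on a stated plan. The SAP names no error term. It gives no SDs, so nothing shows that variances will differ. It does not name A vs B as a primary contrast: the messages are compared by name only in the secondary ANOVAs. If those are two-arm comparisons, arm C never enters the error term, and with two equal arms the pooled and Welch standard errors coincide. If the primary contrasts are all message versus control and the control arm is less variable, the error is conservative and costs a few points of power. If post-message motivation is collected only in A and B, that outcome has no arm C residuals and no control contrast at all.

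Most of this stands as a limit on the claim. A reader might infer that A-versus-B error bars are too narrow and message-versus-control error bars too wide. The documents do not support that as a finding: ceiling effects could reverse it, and different spreads in A and B could break the pattern.

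The objection does not remove the point itself. Planned contrasts in the primary ANCOVA imply a three-arm model, emotionality is rated in all three arms, and nothing in the plan relaxes the equal-variance default. The remedy does not depend on which arm is more variable.

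**Conclusion.** The point holds in conditional form. For any model that contains arm C, default contrasts have the wrong error rate and interval width if residual variances differ, and this design makes a difference plausible.

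With a control/message variance ratio of 0.75 to 0.25, equal variances in A and B and nominal 5%, A vs B has a type I error of about 6% to 9%. Intervals for one message versus control are about 2% to 10% too wide, and those for the averaged messages versus control about 5% to 22%. At a ratio of 1 there is no error, and above 1 the directions reverse. The effect is modest at moderate ratios, so this is a worthwhile improvement and not a fatal flaw. It does not apply to models fitted to A and B only.

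Whether it applies to motivation depends on an unresolved point. Study Procedures can be read as collecting the post-message rating in A and B alone, or as limiting only a perceived-impact question to those arms. The two sections need reconciling, and that is the larger issue for that outcome.

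**What to change.** State in the Statistical Analysis Plan that all contrasts in models containing arm C use HC3 standard errors or one residual variance per arm. This covers the primary ANCOVAs, the emotionality ANOVAs and, if arm C is included, the secondary ANOVAs. Welch tests serve for unadjusted comparisons. For adjusted ones, including the covariate-corrected emotionality analyses that the plan mentions, HC3 or a mixed-model fit with arm-specific variances does the job.

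Alongside this, list the planned contrasts, say which arms enter each model, and reconcile Study Procedures with the Statistical Analysis Plan on whether post-message motivation is collected in arm C.

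The cost is a sentence or two and a different option or procedure in the same software, with no new data. If variances prove equal, almost nothing is lost: in simulation the average HC3 standard error was within 0.5% of the pooled one.
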